**7. REGISTRY ADMINISTRATION**

Existing patient medical records will only be reviewed by study site staff who already have access to the files and who have been trained to the study protocol. Once a qualifying patient medical record is identified, the study site staff member will extract only the required data elements and enter them directly into an Excel database provided by the study Sponsor.

There will be no identifying information entered into the database that could potentially connect an individual data record to an individual patient. Unique de-identified codes will be used for each patient data set entered into the database.

The collected retrospective data will only be used for the purposes of evaluating the primary and secondary objectives of this study.

The parties who will have access to the retrospective data and database will be study site investigators and designated study site staff, the study Sponsor and the study biostatistician.

Access to the database will not be given to outside parties at any time during the data collation and analysis process or in the future for any reason.

**7.1. COMPLIANCE STATEMENT**

The investigators will perform the study in accordance with this protocol. Identification, collection and recording of data will be accurate and will ensure the privacy, health, and welfare of patients during and after the data collection process.

## **7.2. DATA COLLECTION AND MANAGEMENT**

Primary records (source documents) will continue to be maintained in the study site patient medical record files as before. The extracted study data elements will be directly entered into an Excel database to which only the designated study staff, the study Sponsor and the study biostatistician will have access.

### **7.2.1. Confidentiality and Privacy**

Privacy of subjects and confidentiality of the collected data elements will be secured through use of a de-identified coding system that will comprise the first and last name initials of the investigator at a test site followed by the order of entry of the subject's data into the database from 001 onwards, as applicable. For example, the third suitable patient record to be identified at [name] study site would have a de-identified entry code of JB003.

A separate sheet containing the link between the code and the subject's medical file will be maintained in a separate location at each respective test site until such time that all the pertinent data has been collated, entered into the database and double-checked for accuracy and completeness. At this time, all copies of the sheets containing the link between the code and the subject's medical file at each study site will be destroyed.

### **7.2.2. Providing Results to Subjects**

Results will not be provided to subjects as there is no diagnostic or otherwise medical purpose associated with this retrospective analysis that could in any potential way benefit the patients whose data was included in the analysis or alert them to potential risks or issues in any other regard.

## **7.3. REGULATORY AND ETHICAL CONSIDERATIONS**

### **7.3.1. Risk Assessment**

The only potential risk to subjects in this study is breach of privacy and confidentiality. The application of a de-identified coding system to record patient data has been established to minimize this risk.

### **7.3.2. Potential Benefits of Participation**

There is no direct benefit to the study subject from participation in this registry trial. Indirect benefit to potential future patients is the provision of data and information to physicians who treat individuals with NMSC that may enable them to consider non-invasive SRT as a viable treatment option.

### **7.3.3. Risk-Benefit Assessment**

The Risk-Benefit assessment reveals no negatives in conducting this retrospective analysis.

## **7.4. RECRUITMENT STRATEGY**

Initially, eligible study sites will be identified and selected as those who have treated NMSC patients with SRT-100™ prior to January 1, 2015 and for whom follow-up data is available. This study is a pure retrospective analysis. No additional

information will be collected for any subject in this study other than the required information that is already existing in their patient file.

At each study site, designated and trained study staff will perform an initial review of the existing patient charts for those who received a diagnosis of NMSC for which they received SRT-100™ treatment prior to January 1, 2015 and for whom follow-up data is available. From this initial review, selected charts will be further reviewed for the satisfaction of inclusion criteria and presence of required data elements.

## **7.5. INFORMED CONSENT**

This retrospective study meets the criteria for waiver of consent, assent and HIPAA authorization according to the following criteria: 1) There is an adequate plan to protect identifiers from improper use and disclosure; 2) There is an adequate plan to destroy any identifiers at the earliest opportunity; 3) Protected health information (PHI) will not be re-used or disclosed for another purpose; 4) The research could not practicably be conducted without the waiver of privacy authorization; and 5) The research could not practicably be conducted without the use of PHI.

All of the data is collected retrospectively from information already recorded in existing patient medical files.

#### **7.6. PAYMENT TO SUBJECTS**

Patients whose data is collected in this retrospective analysis will not receive payment or any other form of compensation.

#### **7.7. CONFIDENTIALITY**

All data and records generated during this study will be kept confidential in accordance with HIPAA regulations on subject privacy. The Investigator and other site personnel will not use such data and records for any purpose other than conducting the study. Coded de-identifiers will be used for all data entries.

#### **8. SAFETY MANAGEMENT**

Safety management, including adverse event evaluation and reporting, is not applicable to this registry trial as all evaluations are being performed on prior existing data.

#### **9. PUBLICATION**

It is intended that the outcome of this retrospective registry analysis be written up for publication in a peer-reviewed journal. In any potential publication, there will be no identifiable information for any individual subject and no individual case studies will be profiled.

## **10. RESULTS ANALYSIS**

### **10.1. PRIMARY ANALYSIS**

Primary analysis of the retrospective data set will be assessment of cure rates and incidence of reoccurrence of lesions.

#### **10.1.1. Cure Rate**

Cure rate will be calculated as the percentage of lesions that attained complete cure following treatment completion, reported as the overall success rate.

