#### Data/Specimen Collection Procedures and Frequency

- Study data will be retrospectively collected from already existing documentation in patient files at the participating sites.
- Study staff will perform an initial review of the existing patient charts for patients who were treated with SRT-100™ for NMSC prior to January 1, 2015. The selected charts will be further reviewed for satisfaction of inclusion criteria and presence of required data elements. The study staff will extract the required information from the patient charts and enter it into an Excel database provided by the study Sponsor.
- The data elements of patient demographics, lesion diagnostic variables and characteristics, lesion size and margins, treatment duration, treatment dosage and schedule, treatment outcomes (particularly cured vs, non-cured) and follow-up outcome variables (particularly incidence of lesion recurrence) will be recorded.
- Data collection will be ongoing until no additional qualifying patient charts are identified at the respective study sites.

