While formal long-term outcome evaluations may be lacking, there is much existing data. This study will utilize retrospective chart analysis to evaluate the outcomes of SRT-100™ therapy on NMSC lesions over a long-term post-treatment period. Long-term cure rate is considered the primary outcome, with secondary outcome evaluation focused on the impact on cure rate and other treatment outcomes of key variables such as lesion type, location, patient characteristics and treatment parameters such as treatment dosing and fractionation.

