#### **5.1.1. Primary Objective**

The primary objective of this study is to evaluate the treatment outcomes of the retrospective data for long-term safety and efficacy of application of SRT-100™ for the treatment of NMSC (SCC and BCC), including long-term cure rates.

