**F. Follow-Up:**

1. Time in months since the most recent follow-up since end of treatment
2. Recurrence: Yes/No
3. Recurrence treatment and outcome (as applicable)
4. Follow-up notes (as applicable)

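### Long-term cure is the primary outcome, but the headline cure rate is an undated percentage of an undefined 'cured' field, and the Kaplan-Meier analysis that could supply the long-term figure is not named for it and has no recurrence date among its listed data

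*Combined protocol and SAP*

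**What the plan says.** - **Outcome.** Section 2: "Long-term cure rate is considered the primary outcome". The primary objective in 5.1.1 covers long-term safety and efficacy, "including long-term cure rates".
- **Headline formula.** Section 10.1.1: "Cure rate will be calculated as the percentage of lesions that attained complete cure following treatment completion, reported as the overall success rate". No assessment time, minimum follow-up or confidence interval is given.
- **Data.** The Abstract (Data/Specimen Collection) separates "treatment outcomes (particularly cured vs, non-cured) and follow-up outcome variables (particularly incidence of lesion recurrence". Section 6.3 keeps the same split: an undated yes/no *Cured* field under E (Outcomes), and under F (Follow-Up) "Recurrence: Yes/No", "Time in months since the most recent follow-up since end of treatment" and "Recurrence treatment and outcome (as applicable", plus free-text notes. No date or month of recurrence is listed.
- **Recurrence analysis.** Section 10.1.2, within the primary analysis, plans Kaplan-Meier estimates by follow-up year with 95% confidence intervals, a log-rank test between lesion types and a Cox regression. It names no year or value as the long-term cure rate and does not say how lesions recorded as not cured enter the curve.
- **Link to charts.** Under 7.2.1, once the data are entered and checked, all sheets linking each code to the subject's "medical file at each study site will be destroyed".

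**The concern.** The declared outcome is long-term, but the number that will carry the success label has no time attached. If *Cured* records clearance at the end of treatment, a lesion that clears and recurs two years later still counts as a success. A reader who knows the stated objective could take that percentage for long-term cure.

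The Kaplan-Meier curve could answer the long-term question, but it needs the time at which each recurrence occurred. The listed fields give only whether a lesion recurred and how long the patient was followed. The form also records how the recurrence was treated and with what result, so the last visit can fall after the recurrence. Dating recurrences at that visit would shift the yearly estimates, and the log-rank and Cox analyses would use the same wrong times.

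**Working it through.** The plan states no target cure rate, sample size or event count, so there is no figure of its own to reproduce. The sizes below are illustrations. They use the recurrence quoted in section 3 from the similar earlier study: 1.9% at 2 years and 5.0% (95% CI 3.2%–6.7%) at 5 years. Initial cure, follow-up length and the lag from recurrence to last visit are assumptions, because the documents give none of them.

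**1. Headline gap under the clearance reading.** Gap = p × r, where p is the initial cure proportion and r is 5-year recurrence among cleared lesions.

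| p | r = 3.2% | r = 5.0% | r = 6.7% |
|---|---|---|---|
| 0.90 | 2.88 | 4.50 | 6.03 |
| 0.95 | 3.04 | 4.75 | 6.37 |
| 1.00 | 3.20 | 5.00 | 6.70 |

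Values are percentage points. At p = 0.95 the 10.1.1 figure is 95.0%, while 0.95 × 0.95 = 90.25% are cleared and recurrence-free at 5 years.

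**2. The other reading.** Suppose *Cured* means no recurrence up to the last chart entry, and every lesion clears. The percentage then mixes follow-up lengths. Simulated crude recurrence was 3.0% for follow-up uniform on 0–6 years, 4.0% for 0–8 years, 2.4% for exponential with mean 2.5 years capped at 8, and 5.5% for uniform on 3–8 years. The 5-year value is 5.0%. The headline is not a rate at any stated time under this reading either.

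**3. Recurrences dated at last follow-up.** Recurrence time T has hazard −ln(0.981)/2 = 0.00959 per year to year 2, then −ln(0.950/0.981)/3 = 0.01070, with cumulative hazard H and distribution function F. Planned end of follow-up C is independent of T, with hazard h_C = 1/m (exponential, mean m) or 1/(b−u) (uniform on 0–b). A recurrent lesion is last seen at the earlier of C and T + L, where L is the lag. The Kaplan-Meier cumulative hazard at t is then

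Λ(t) = H(t−L) + ∫₀ᵗ h_C(u) [F(u) − F(u−L)] / [1 − F(u−L)] du,

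and the reported recurrence is 1 − exp(−Λ(t)). With L = 0 it returns 1.9% and 5.0%. If last follow-up is unrelated to recurrence, it becomes Λ(t) = ∫₀ᵗ h_C(u)F(u)du.

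| Follow-up (years) | 2-year %, L = 3/6/12 months | 2-year %, unrelated | 5-year %, L = 3/6/12 months | 5-year %, unrelated |
|---|---|---|---|---|
| Exponential, mean 2 | 1.89/1.84/1.66 | 0.95 | 5.34/5.64/6.15 | 5.96 |
| Exponential, mean 3 | 1.81/1.70/1.43 | 0.63 | 5.14/5.26/5.43 | 4.01 |
| Exponential, mean 4 | 1.77/1.63/1.31 | 0.48 | 5.04/5.07/5.07 | 3.02 |
| Exponential, mean 5 | 1.75/1.59/1.24 | 0.38 | 4.98/4.95/4.85 | 2.43 |
| Exponential, mean 6 | 1.74/1.57/1.19 | 0.32 | 4.94/4.88/4.71 | 2.03 |
| Uniform 0–6 | 1.75/1.60/1.25 | 0.41 | 5.18/5.36/5.66 | 5.53 |
| Uniform 0–8 | 1.73/1.55/1.16 | 0.29 | 4.98/4.96/4.88 | 2.77 |
| Uniform 0–10 | 1.71/1.52/1.12 | 0.22 | 4.91/4.82/4.61 | 1.88 |
| Uniform 0–12 | 1.70/1.50/1.09 | 0.18 | 4.88/4.74/4.46 | 1.43 |

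Simulations of five of these patterns (exponential means 2, 3 and 5; uniform 0–8 and 0–10) agree within 0.1 point. For four mid-range patterns (exponential means 3 and 5; uniform 0–8 and 0–10), a lag of 3–12 months gives 4.6–5.4% at 5 years and 1.1–1.8% at 2 years. Over all nine the ranges are 4.5–6.2% and 1.1–1.9%.

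The 2-year value is understated in every row. That depends on mean follow-up of 2 years or more: with an exponential mean of 1 year, the same lags give 2.11/2.25/2.36%, which is too high.

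**The case against.** The strongest reply has four parts.

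- **'Cured' is not defined as clearance.** Complete cure following treatment could cover any later time, and charts are read to the most recent entry (5.3.1), so an abstractor might code *Cured* with later recurrence in mind. This stands. A reader might infer that 10.1.1 certainly reports initial clearance, but the documents make that only the natural reading. The headline gap is therefore conditional. The missing time point and interval are not.
- **Recurrence is already in the primary analysis.** This also stands. A reader might infer that the plan ignores long-term outcome, but 10.1 and 10.1.2 include yearly estimates with confidence intervals. What is missing is a statement that one of those values is the long-term cure rate, and how non-cured lesions enter.
- **The date may exist.** Section 6.3 uses short labels, the sponsor's database is not in the documents, and the notes or the recurrence-treatment entry could hold a date. So the supportable claim is that no recurrence date is listed, not that none will be available. Optional free text is still a weak basis for a time-to-event analysis.
- **The event-date bias may be small.** If follow-up stops soon after recurrence, the 5-year error is mostly about half a point or less. This stands for the mid-range patterns. It does not remove the 2-year error, nor an error of about one point at 5 years when follow-up is short and the lag is 12 months.

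**Conclusion.** The point holds and should be fixed. The plan declares a long-term outcome and gives its headline label to a percentage that is not tied to any time. The analysis that could supply the long-term figure lacks a designation, a rule for non-cured lesions and a listed event date.

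Under the clearance reading, with 90–100% initial cure assumed, the headline exceeds 5-year durable cure by 4.5–5.0 points (2.9–6.7 over the cited interval). The event-date error rests on an assumed lag. It is zero if the last visit is the one that found the recurrence, and modest at 5 years but visible at 2 years for lags up to 12 months. It is large if follow-up is unrelated to recurrence (1.4–6.0% at 5 years against 5.0%, and 0.2–1.0% at 2 years against 1.9%). At 5 years it can run in either direction.

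A reader might go further and conclude that the Kaplan-Meier results will be unusable. The documents do not support that, because they say neither how long lesions are followed after recurrence nor what the free text contains.

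**What to change.** 1. **Section 10.1.1.** Define 'cured' and when it is assessed. Report the percentage with a 95% confidence interval as initial clearance, not as the overall success rate.
2. **Section 10.1.2.** Designate as long-term cure the Kaplan-Meier probability at named years after the end of treatment (for example 2 and 5), with 95% confidence intervals, and state how non-cured lesions enter. One workable choice is to count them as failures at time 0 among all eligible treated lesions. The curve among cleared lesions would then also be reported for comparison with the cited study, whose abstract gives recurrence rates and does not say that never-cured lesions were counted as failures.
3. **Section 6.3 F.** Add month of first recurrence after the end of treatment, and fill it in before the link sheets are destroyed. Use it as the event time in the Kaplan-Meier, log-rank and Cox analyses. Report how many recurrences remain undated, with a sensitivity analysis placing them at the earliest and latest possible month.

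The cost is some wording and one extra chart look-up per recurrent lesion, about 5% of lesions if the cited 5-year rate applies. Under the clearance reading, the sponsor must also accept a somewhat lower headline figure.

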#### **A. Patient Information and Demographics:**

1. Gender
2. Age at treatment start

3. Ethnicity
4. Significant comorbidities

B. Lesion Diagnostic Variables and Characteristics:

1. Pathology diagnosis
2. Diagnosis subtype/variant
3. Other pathology
4. Recurrent lesion (yes/no)
5. Previous treatment if recurrent
6. Lesion location (no restrictions): scalp, mastoid, forehead, cheek, nose, ear, chin, lips, neck, upper arm, lower arm, hand, upper leg, lower leg, foot.

C. Lesion Size and Margins:

1. Lesion size
2. Treatment margin
3. Lead cutout size
4. Applicator size

D. Treatment Dosage and Schedule:

1. Treatment dose
2. Number of treatments
3. Number of treatments per week
4. Treatment span(days)

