5. TDF
6. TX energy KV: 50, 70, 100
7. Total dose
8. Break duration (days or N/A)

E. Outcomes:

1. Cured: Yes/No
2. Adverse Events: yes, no
3. Adverse Events description (as applicable)
4. Notes (as applicable)

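### The cure rate depends on treatment completion, but no field records completion, so its denominator is open and the dose terms may partly reflect early stopping

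*Combined protocol and SAP*

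**What the plan says.** Section 10.1.1 gives the primary rate as the "percentage of lesions that attained complete cure following treatment completion", and presents it as the overall success rate. It does not define completion, state the denominator, or say how a course that stopped early is counted.

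Section 6.3 D lists eight treatment items. They include "1. Treatment dose", "2. Number of treatments" and "Number of treatments per week", followed by span, TDF, energy, total dose and break duration. Each is a single value. None is marked as planned or delivered, and there is no completion status or reason for stopping. Section 6.3 E holds a two-level cure field, adverse events and optional notes. Section 6.3 F holds follow-up time from the end of treatment, recurrence and notes.

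Section 10.1.2(iii) enters total treatment dosage and TDF in the Cox model for recurrence-free survival, with no term for completion. The relation of outcome to dose and fractionation is a secondary objective (Abstract and section 5.1.2).

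Section 7.2.1 provides that, once the data have been entered and double-checked, "all copies of the sheets containing the link between the code" and the patient's file are destroyed at every site.

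**The concern.** The primary endpoint refers to a condition that the database cannot identify. Consider a lesion whose course ended early because of a skin reaction, frailty or progression. Three site behaviours fit the text:

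- leave the lesion out, because treatment was not completed;
- enter it as not cured, because cure after completion was impossible;
- enter it by the response in the chart.

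The first makes the reported rate a completers' rate, which is too high as a statement about lesions treated. The second counts recorded cures as failures, which is too low. Sites may differ, and the analyst cannot sort the records afterwards.

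The dose question follows from the same gap. If the dose fields hold what was given, a low total dose or TDF can mean either a smaller planned course or a course cut short. Where stopping goes with a worse prognosis for other reasons, the Cox model can show a dose-response that the treatment did not cause.

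**Working it through.** **1. Can completion be reconstructed from the fields?** The product of dose per treatment and number of treatments gives a total, but there is no plan to compare it with. Break duration describes an interruption; it does not record permanent stopping. Notes are optional free text. Completion therefore cannot be derived reliably.

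**2. Do the eligibility rules settle the denominator?** Section 5.4.1 requires treatment with the device (criterion 2), not a completed course. The only exclusion in section 5.4.2 is another lesion etiology. Criterion 7 requires sufficient data without defining sufficient, which leaves an unlogged route for incomplete courses to be dropped. Nothing settles the matter.

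**3. Effect on the cure rate.** The plan states no target rate or sample size, so there is no figure to reproduce. Every input here is an assumption: cure among completers p = 0.98, share stopped early f = 2-10%, cure among those stopped c = 0-80%.

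All-treated rate = p(1 − f) + c·f

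- f = 0.02, c = 0.80: 0.9604 + 0.0160 = 0.9764 (97.6%)
- f = 0.05, c = 0.50: 0.9310 + 0.0250 = 0.9560 (95.6%)
- f = 0.10, c = 0.80: 0.8820 + 0.0800 = 0.9620 (96.2%)
- f = 0.10, c = 0: 0.8820 + 0 = 0.8820 (88.2%)

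If stopped courses are omitted, the reported rate is 98%, too high by f(p − c): from 0.02 × 0.18 = 0.36 points to 0.10 × 0.98 = 9.8 points.

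If all are entered as not cured, the reported rate is too low by c·f: from 0 to 0.10 × 0.80 = 8.0 points.

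Both errors go to zero as f goes to zero. For scale, the retrospective study summarised in section 3 reports 5.0% recurrence at 5 years, so a shift of 2 points would not be small beside the failures being counted.

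**4. Effect on the dose terms, direction only.** A simulation used 2,000 lesions per run and 100 runs per setting. The baseline hazard was −ln(0.95)/5 = 0.0103 per year, taken from that 5.0%. Planned dose had no true effect. Stopped courses received 30-90% of the planned dose and had 2 or 3 times the hazard for reasons other than dose.

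| Share stopped | Covariates | Hazard ratio per 10% more dose | Runs with p < 0.05 |
|---|---|---|---|
| 0% | delivered dose | 1.00-1.01 | 4-6% |
| 3-10% | delivered dose | 0.83-0.93 | 21-90% |
| 3-10% | planned dose and completion flag | 0.97-1.01 | 2-10% |

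A separate simulation used 30,000 lesions per setting, 2-10% stopped at 30-80% of planned dose, and 3-5 times the hazard. Delivered dose alone gave 0.56-0.75 per 10 Gy. Adding a completion flag to delivered dose gave 0.98-1.09. The artefact can therefore be removed without replacing delivered dose in the model. A few fits in the first simulation did not converge cleanly, and neither simulation estimates this registry's bias.

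**The case against.** **The denominator may already include everyone.** The completion phrase can be read as saying when cure was attained, so that a stopped course stays in and counts as a failure. Section 5.3.2 also says that data from every qualifying subject are included. A reader might infer from section 10.1.1 that stopped courses are excluded and the rate favours the device. The documents do not support that: they neither direct exclusion nor fix the direction of error. What stands is that the denominator is unstated, and that the alternative reading turns recorded cures into failures.

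**Safety is covered.** A reader might infer that courses stopped for toxicity disappear from the safety results. Section 6.3 E has adverse event fields, and section 10.1.2 covers events during both treatment and follow-up. Those events are lost only if the whole lesion is omitted.

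**Gross truncation would show.** Section 10.2.4(ii) tabulates the number of treatment visits, so markedly short courses would be visible. This stands in part: modest truncation and the reason for stopping would not be.

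**The dose fields may hold the planned dose.** They are unlabelled. If sites enter the plan, the early-stopping mechanism does not arise, but stopped courses are then credited with dose they never received. Sites may also differ.

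**The simulations assume what they show.** This is fair. The excess hazard and the nil dose effect were put in, and no stopping rate or hazard appears in the documents.

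**Delivered dose is a legitimate exposure.** This also stands. A reader might infer that planned dose should replace it as the main Cox term. That is a debatable choice of estimand, and the stated objective does not require it.

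**Conclusion.** The gap is real and confined to data capture and analysis wording. The primary rate refers to completion, no field records it, and the check becomes impossible once the link sheets are destroyed. The reported rate may be too high or too low depending on site practice. The range of 88.2% to 97.6% rests entirely on assumed stopping and cure rates, and its lower end is a corner case: 10% stopping with none cured. The dose-response concern holds only if the recorded dose is the delivered dose and stopping is linked to prognosis in ways other than through dose. If few courses stopped early, neither effect matters, but without a completion field the registry could not show that. This is a cheap improvement; it does not show that the results are biased.

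**What to change.** Before the link sheets are destroyed:

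1. **Section 6.3 D.** Add a field for course completed as planned (yes, no, not documented), the reason if not, and the planned number of treatments and planned total dose where the chart shows them. Label the existing dose fields as delivered.
2. **Section 10.1.1.** Set the denominator to all eligible lesions that received at least one SRT-100 treatment, each counted by its recorded Yes/No cure outcome. Report the completers-only rate as secondary.
3. **Section 10.1.2(iii).** Keep delivered total dose and TDF. Add course completion as a covariate, or run a completers-only sensitivity analysis. Use planned dose as a further sensitivity analysis where available. If low dose itself causes recurrence, a completion term may absorb part of that effect, so show the model with and without it.

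The cost is a little more abstraction time per chart, some entries of not documented (because only existing records may be used), and possibly a slightly lower stated success rate. No treatment rule changes.
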